6.1 General recording items

Name, gender, age, contact information, brief medical history, vital signs, physical examination, etc.

6.2 Diagnostic indicators

Tumor pathology, staging, symptom-based anorexia assessment, TCM evidence.

6.3 Main observational indexes: refer to the "Anorexia Diagnosis and Treatment Pathway" of the Professional Committee of Tumor Nutrition and Supportive Therapy of the Chinese Anti-Cancer Association.

① Symptom-based anorexia evaluation form: Appendix I.

② Simplified Appetite Scale: Appendix V.

6.4 Secondary observation indicators:

① Fatigue Symptoms Scale: Appendix III.

② Patient's expectation of acupuncture: Appendix II. Appendix II

Appetite level: VAS is a semi-quantitative assessment of the degree of anorexia nervosa.

Drawing on the practice of foreign countries in the last century and the idea of VAS assessment for cancer pain in China, it is suggested that a 10 cm long travel scale with 10 scales on one side and "0" and "10" marks on the other side should be used. The scale has 10 marks on one side, with the "0" and "10" markings on both ends, with the "0" marking indicating a normal appetite and the "10" marking indicating an extreme aversion to food. When using the graduated side of the back to the patient, let the patient in the ruler marked on the degree of their desire for food on the corresponding position, the physician according to the position marked by the patient for its score, clinical evaluation to "0-2" is "normal appetite / basic normal eaters The clinical assessment is "0-2" as "normal appetite/basic normal eater", "3-5" as "mild anorexia", "6-8" as "moderate anorexia", and >8 as "anorexia". The score of "3-5" was classified as "mild anorexia", "6-8" as "moderate anorexia", and ">8" as "severe anorexia". The efficacy of the treatment was evaluated according to the change in appetite. Effective: improvement level greater than or equal to 1; stable: no change in level; ineffective: decrease in level.

④ Weight. Weight changes caused by factors other than fluid accumulation in the body cavity and swelling. Improvement: weight gain >2Kg and maintained for more than 4 weeks. Stable: weight gain or loss of ≤ 2 Kg. deterioration: weight loss of >2Kg. 5.

⑤ Karnosky Score: Karnosky Physical Condition Score, refer to Appendix IV. Evaluation method: Comparison of scores before and after treatment. Significant effect: more than 20 points higher than before treatment; Effective: more than 10 points higher than before treatment; Stable: less than 10 points higher than before treatment or no change; Ineffective: decrease in weight after treatment compared with before treatment.

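### The only efficacy rule given for the appetite VAS is change of band, which can rank a 1-point gain above a 2-point gain; the SAP does not say whether the raw score or the grade is tested.

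*Protocol*

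**What the plan says.** Appetite level by VAS falls under "6.4 Secondary observation indicators" in the protocol. The instrument is "a 10 cm long travel scale with 10 scales on one side", with 0 as normal appetite and 10 as extreme aversion. The patient marks a position with the graduations turned away, and the score is set by "the physician according to the position marked by the patient for its score". Nothing says whether it is recorded in whole numbers or decimals, or how a mark between graduations is rounded.

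The bands are given as "The clinical assessment is '0-2' as 'normal appetite/basic normal eater", and then: "The score of '3-5' was classified as 'mild anorexia', '6-8' as 'moderate anorexia', and '>8' as 'severe anorexia". Efficacy follows from the change of band: "Effective: improvement level greater than or equal to 1; stable: no change in level; ineffective: decrease in level".

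The SAP, section 2 (Statistical analysis plan), describes measures at each visit by mean and SD and compares changes by paired t-test and ANOVA. It describes count data by frequencies and analyses them by chi-square or a nonparametric test. It assigns no individual indicator to either route. Tests are two-sided at 0.05. Protocol section 2 sets 30 per group as an exploratory number, without a power calculation.

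**The concern.** A change-of-band rule depends on where a patient starts within a band as well as on how far the patient moves, so the order of outcomes can be reversed. It also reduces a 0-10 reading to three categories, which costs information in a trial of 60 patients.

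Two omissions add to this. The SAP leaves two analyses open, so the choice between raw score and grade could be made after the data are seen. The missing resolution rule also matters, because rounding up, down or to nearest moves marks across the cut-points that define a success. The physician assigns the score, the control is conventional care without a sham, and the documents describe no blinding of the assessor.

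At stake is a clear result on a direct rating of appetite, which is the subject of the research objective.

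**Working it through.** The plan states no effect size, SD or power for the VAS, so there is no figure of its own to reproduce.

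**1. Ordering, with no assumptions.** In whole numbers the bands are 0-2, 3-5, 6-8 and 9-10.

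| Change | Points gained | Bands | Grade |
|---|---|---|---|
| 6 to 5 | 1 | moderate to mild | effective |
| 8 to 6 | 2 | moderate to moderate | stable |
| 3 to 2 | 1 | mild to normal | effective |
| 5 to 3 | 2 | mild to mild | stable |

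This occurs with whole-number scores and does not depend on any rounding rule.

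**2. Gaps.** Whole-number scores 0 to 10 are 11 values, and the four bands cover 3 + 3 + 3 + 2 = 11. There is no gap. If decimals are recorded, the intervals between 2 and 3 and between 5 and 6 have no band: 2 of 10 cm, or 20% of the ruler. Under the assumptions in step 3, about 28% of follow-up scores would fall there.

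**3. Power.** From the documents: 30 per arm, two-sided 0.05. Assumed: baseline mean 6, SD 1.8, truncated to 3-10; control follow-up mean 5.5, SD 2, truncated to 0-10; correlation 0.5; true benefit 1.2 or 1.5 cm. In the simulation, scores were rounded to whole numbers before banding, so the gaps play no part in these results.

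| Analysis | 1.2 cm | 1.5 cm |
|---|---|---|
| Three grades, chi-square | 36% | 56% |
| Three grades, rank test | 47% | 68% |
| Change in raw score, t-test (ANOVA with two groups) | 68% | 87% |
| Raw score, ANCOVA on baseline | 75% | 90% |

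Repeat simulations moved these figures by up to about 3 points.

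A normal approximation that ignores truncation checks the last two rows. Power is about Φ(d·√(30/2) − 1.96).
- SD of change = √(1.8² + 2² − 2·0.5·1.8·2) = √3.64 = 1.91. At 1.2 cm, d = 0.63 and power is about 68%. At 1.5 cm, d = 0.79 and power is about 86%.
- ANCOVA residual SD = 2·√(1 − 0.5²) = 1.73. At 1.2 cm, d = 0.69 and power is about 76%. At 1.5 cm, d = 0.87 and power is about 92%.

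**4. Where the loss comes from.** At 1.2 cm the distance from ANCOVA to chi-square is 75 − 36 = 39 points: 7 from baseline adjustment (75 − 68), 21 from banding (68 − 47) and 11 from chi-square instead of the rank test (47 − 36). At 1.5 cm it is 34 = 3 + 19 + 12.

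**5. Sensitivity.** A wider set used 36 scenarios: baseline mean 5.5 or 6.5, SD 1.5 to 2.5, correlation 0.3 to 0.7, control improvement 0.5, extra benefit 1.0 or 1.5. The t-test on raw change had more power than the graded tests in all 36. The loss was about 8 to 41 points for a chi-square test of effective against not effective, and about 5 to 34 points for a rank test on the three grades.

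**The case against.** The case against making much of this is substantial.

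- **A reader might infer that the VAS will be analysed only by band.** The documents do not establish that. The SAP's mean, SD and ANOVA wording neither names nor excludes the raw VAS. What stands is that the band rule is the only one specific to the VAS, and that the choice is left open.
- **A reader might infer that some scores cannot be graded.** That holds only for decimal readings. A ruler with ten marks, in a measure the protocol calls semi-quantitative, fits whole-number scoring, and then the >8 band simply means 9 and 10. What stands is that no resolution is stated. The gap and the power figures should not be added together, since the power figures assume rounding.
- **A reader might attribute the whole distance between ANCOVA and chi-square to banding.** Part comes from baseline adjustment, which the SAP does not plan, and part from the weaker of two permitted tests. Banding alone costs about 20 points in the worked example.
- **A reader might infer that the scale will be answered backwards,** because the patient is said to mark "marked on the degree of their desire for food on the corresponding position" while the upper end is the "marking indicating an extreme aversion to food". Both anchors are stated explicitly and the text reads as a translation, so this is probably a wording artefact. The wording shown to patients is not in the documents.

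The VAS is also one of several secondary indicators in an exploratory trial. Two main indexes, the symptom-based form and the simplified appetite scale, already cover appetite. This limits the weight of the point, but it does not remove the ordering problem or the open choice of analysis.

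**Conclusion.** The point holds as a cheap improvement to a secondary indicator. The ordering anomaly follows directly from the printed bands and needs no assumption. The SAP's silence on which route applies is a matter of text. The missing resolution rule is real, but gaps follow from it only if decimals are recorded.

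The power loss is conditional. Against the better of the two kinds of test that the SAP allows for graded data, banding costs about 20 points at 30 per arm with a benefit of 1.2 to 1.5 cm. Across the wider set of assumptions the loss against a rank test was about 5 to 34 points. Its direction was the same in every scenario; its size rests on an SD, correlation and effect that the documents do not give. No primary conclusion of the trial depends on the VAS grades.

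**What to change.** - In the SAP, name the between-arm ANCOVA of the raw 0-10 VAS score, adjusted for baseline, as the efficacy analysis of this indicator, and name the visit it applies to. A baseline reading is already needed for the band rule.
- In protocol 6.4 and the CRF, require the raw score to be entered as well as the grade. State the resolution that the ruler supports. If its ten marks are evenly spaced they are 1 cm apart, so recording to 0.1 cm would need a finer instrument.
- State a rounding rule, or restate the cut-points, so that the bands are contiguous.
- Keep effective, stable and ineffective as description only.

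The cost is wording in the protocol, SAP and CRF. The CRF was not supplied, so whether it already holds the raw score could not be checked. No extra patients or visits are needed. One small downside is that the headline becomes a mean difference instead of an effective rate, which can still be tabulated.

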6.5 Provisions on the time point of follow-up

6.5.1 Data collection before enrollment

Medical record collection: fill in the baseline data according to the requirements of the CRF form;

Chinese medicine evidence: identify according to the Chinese medicine identification criteria and check the box on the CRF table;

Vital signs, physical examination;

blood, urine, stool routine, liver function, kidney function (within 2 weeks before enrollment);

Imaging examination: chest radiograph or chest CT, abdominal B ultrasound or abdominal or pelvic CT (within 1 month before enrollment).

6.5.2 Data collection at 2 weeks and 4 weeks of enrollment

Medical record collection: symptom-based anorexia assessment form, simplified appetite scale, fatigue symptom scale, appetite level, body weight, and Kahn's score according to the CRF form.

Therapeutic use of medications

TCM evidence: identify according to TCM identification criteria, check on the CRF form;

Vital signs, physical examination;

blood, urine, stool routine, liver function, kidney function (within 2 weeks);

6.5.3 Data collection 8 weeks after enrollment

Medical record collection: fill in the symptom-based anorexia assessment form, simplified appetite scale, fatigue symptom scale, appetite level, body weight, Kahn's score according to the requirements of CRF form.

Medication use for treatment

Tumor efficacy capture.

TCM evidence: identification according to TCM identification criteria, checked on the CRF form;

Vital signs, physical examination;

Blood, urine and stool routine, liver function, kidney function (within 2 weeks);

Imaging examination: chest radiograph or chest CT, abdominal B ultrasound or abdominal or pelvic CT (within 1 month).

7 Adverse events

7.1 Record of adverse events

During the clinical study, truthfully fill in the adverse event record form, record the occurrence time, severity, duration of the adverse event to take effective measures and regression.

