5.2 Treatment program

5.2.1 Ear acupuncture group

Ear acupuncture treatment + conventional nutritional support and symptomatic treatment (refer to "Diagnostic and therapeutic path of anorexia nervosa" of tumor nutrition and supportive therapy committee of China Anti-Cancer Association).

Commonly used main points: Shenmen, stomach, spleen, subcortex.

Auxiliary points: Sanjiao, sympathetic, liver, small intestine.

Methods: Embed an earring needle and fix it with adhesive tape, press each point for about 2 minutes each time, 2-3 times a day, the pressure depends on the tolerance of the individual, alternating between the two ears, 2-3 times a week, 4 weeks of treatment, observation until 8 weeks.

5.2.2 Control group: Conventional nutritional support and symptomatic treatment.

During the treatment period, both groups can use supportive therapy reciprocally, if there are treatment-related adverse events, they should be handled separately, and the causes, history, symptoms and treatment measures should be recorded in detail. During the treatment period, both groups of cases could adopt the international standard protocol (Version 3.2014 NCCN) with or without standard chemotherapy or or without standard chemotherapy or radiation therapy.

6 Observation Indicators

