Safety analysis: the X test was used to compare the incidence of adverse events in the two groups, and the adverse events occurred in this trial were described in a list. Adverse events: the X test was used to compare the incidence of adverse events in the two groups, and the adverse events occurred in this trial were described in a list; the changes of normal/abnormal laboratory test results before and after the trial were analyzed, as well as the relationship between the abnormal changes and the test drug. Safety analysis: The X test was used to compare the incidence of adverse events in the two groups and to describe the adverse events in this trial.

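### Adverse events are recorded ad hoc, with no enquiry on the visit lists, and only the needling arm has 2-3 sessions a week, so the two-arm incidence test is open to detection bias

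*Protocol*

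**What the plan says.** - **Recording.** Protocol section 7.1: "During the clinical study, truthfully fill in the adverse event record form". It asks for timing, severity, duration, action and outcome. Section 7.4 adds handling and reporting. Neither section names a visit, a standard question or a recall period.
- **Visit lists.** Section 6.5.2 (weeks 2 and 4) itemises the "symptom-based anorexia assessment form, simplified appetite scale, fatigue symptom scale, appetite level, body weight, and Kahn's score", then medication use, TCM signs, vital signs, physical examination and laboratory tests. Section 6.5.3 (week 8) repeats this and adds tumour response and imaging. Adverse events are on neither list.
- **Contact, needling arm.** Section 5.2.1: needles are embedded, "alternating between the two ears, 2-3 times a week, 4 weeks of treatment, observation until 8 weeks".
- **Contact, control arm.** Section 5.2.2: "Control group: Conventional nutritional support and symptomatic treatment". There is no sham and no matched contact.
- **Analysis.** SAP section 2, safety analysis, plans a chi-square test to "compare the incidence of adverse events in the two groups", plus a listing. Nothing there deals with unequal ascertainment.
- **Numerator.** Protocol section 7.3 counts only events in causality grades 1 to 3, judged by five indicators that are worded for a drug.

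**The concern.** A comparison of recorded incidence is a comparison of true incidence only if events have the same chance of being recorded in both arms. Here recording depends on somebody hearing of the event, and one open-label arm has many more scheduled occasions for that. Protocol section 7.2 describes mild events as usually short-lived. Those are the events a control patient is most likely to have forgotten by a visit two or four weeks later, at which no listed item asks about them. At equal true rates, the needling arm could then record more events, and the planned test would have no means of separating a detection effect from an effect of the needle.

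**Working it through.** The plan states no adverse event rate, no detection probability and no power figure for this test, so there is no figure of its own to reproduce. The check is a comparison of schedules, followed by an illustration on assumed inputs.

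**1. Scheduled trial contacts after enrolment** (Protocol 5.2.1, 5.2.2, 6.5.2, 6.5.3)

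- Needling sessions: 2 × 4 = 8 to 3 × 4 = 12.
- Shared visits: weeks 2, 4 and 8, so 3 in each arm.
- Needling arm: 8 + 3 = 11 to 12 + 3 = 15. Control arm: 3.

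This treats sessions and visits as separate occasions and sessions as staff contacts. The Protocol does not say who places the needles; staff involvement is inferred from the embedding and taping. The imbalance is confined to the 4 treatment weeks. From week 4 to week 8 the trial schedules are the same.

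**2. Which events are exposed**

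| Type of event | How it is found | Equal between arms? |
|---|---|---|
| Laboratory abnormality | Tests at weeks 2, 4 and 8 | Yes |
| Symptom covered by a scale or TCM sign (e.g. vomiting, fatigue) | Asked at the same visits | Yes for the scale; not assured for the adverse event form |
| Other symptom, or mild transient event | Volunteered or noticed at a contact | No |

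**3. Illustration** (all rates assumed; all-cause incidence)

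Recorded incidence = true incidence × probability of detection. With the same true incidence in both arms, the spurious difference = true incidence × (needling detection − control detection).

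- Central case, true 30%, detection 90% v 60%: 0.30 × 0.90 = 0.27; 0.30 × 0.60 = 0.18; difference 9 points.
- Low end, true 20%, detection 80% v 70%: 0.20 × 0.10 = 0.02, or 2 points.
- High end, true 40%, detection 95% v 50%: 0.40 × 0.45 = 0.18, or 18 points.

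**4. Effect on the test**

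The probability of rejection was obtained by summing the product of two binomial probabilities (30 per arm, Protocol section 2) over all tables where the uncorrected two-sided chi-square test rejects at 0.05 (SAP section 2).

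| True rate, both arms | Detection, needling v control | Recorded | Rejection probability |
|---|---|---|---|
| 30% | 90% v 90% | 27% v 27% | 4.9% |
| 20% | 80% v 70% | 16% v 14% | 5.8% |
| 30% | 90% v 60% | 27% v 18% | 12.9% |
| 40% | 95% v 50% | 38% v 20% | 33% |

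With equal detection (50% to 100%) and true rates of 20% to 60%, the rejection probability stays between 4.8% and 5.4%, so the excess comes from the detection gap.

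**5. What the illustration does not describe**

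The section 7.3 numerator is restricted to causality grades 1 to 3. Under it, equal true rates in a needled and an un-needled arm are not a natural starting point. The figures above therefore concern all-cause incidence, not the planned statistic.

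**The case against.** The strongest reply is that the bias is possible but not shown.

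- **Other contacts.** Patients may be inpatients (Protocol section 3), and both arms may receive chemotherapy, radiotherapy and supportive care (section 5.2.2), so the control arm is not seen only three times. This stands, and it shrinks the gap. It does not close it: outpatients are eligible, and background contacts shared by both arms do not cancel 8 to 12 extra sessions in one.
- **Who changes the needles.** Not stated. This stands as a limit; staff contact is the natural reading of the procedure, but it is an inference.
- **The case report form may hold an adverse event page at each visit.** The visit lists refer to that form, which is not among the documents. It cannot be ruled out, but the lists are detailed and do not include the item.
- **Causality grading separates needle effects.** Section 7.3 does aim at this. But its indicators concern drug exposure, stopping and re-exposure, and cannot be applied alike to a control arm without needling. Grading also cannot recover events that were never recorded.
- **Exploratory trial of 60 patients, with events also listed.** True, and it limits the consequences. The test is still planned.

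A reader might go further and infer that the comparison is certain to show more events under needling, or that a benefit such as less vomiting would be hidden. The documents support neither. The first would need detection rates that nobody has. As to the second, vomiting is scored on the anorexia form (Appendix I), and nausea and vomiting are among the TCM signs (section 3.1.2.1); both are assessed in both arms at weeks 2, 4 and 8, so a benefit would show there.

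**Conclusion.** The point holds as a risk built into the plan as written: the between-arm incidence test is open to detection bias, mainly against needling, for symptoms and mild transient events. Laboratory events are not affected. The direction is firmer than the size and rests on needle changes being staff contacts. The size cannot be derived from the documents; the assumed all-cause cases give a spurious difference of 2 to 18 points, with 9 points (27% v 18%) in the central case. A correction is worth making because it is cheap, but the evidence does not justify saying that the result will be biased.

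**What to change.** 1. Add to the lists in Protocol sections 6.5.2 and 6.5.3, for both arms, one identical open adverse event question with a fixed recall period: since the last scheduled visit (at week 2, since enrolment).
2. Add a field to the adverse event form showing whether each event was elicited at a scheduled visit or found at a needling contact.
3. State in the SAP that the between-arm chi-square comparison uses visit-elicited events of any cause. Naming the numerator matters, because the grade 1 to 3 rule of Protocol section 7.3 cannot be applied alike to both arms. Graded events can still be described.
4. List events found only at needling sessions separately, for that arm.

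Recording and care of events at any time stay as they are.

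The cost is one line in each of two visit lists, one tick-box and a short SAP passage. The downside is that short events forgotten by the visit leave the comparison, though they stay in the listing. Some differential recall may also remain, since needled patients may already have talked about their events with staff. Separately, SAP section 1 defines the safety set by use of the study drug, which read literally leaves out the control arm. This change does not cure that; it needs its own correction before the test can be run.

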7.2 Judgment of severity

Mild: usually transient and does not affect normal daily activities.

Moderate: considerable discomfort that interferes with normal daily activities.

Severe: unable to carry out normal daily activities.

7.3 Judgment of causality with drugs

Indicators of causal judgment for adverse event determination:

- Whether there is a reasonable sequential relationship between the time of initiation of the drug and the appearance of the suspected adverse event;
- Whether the suspected adverse event is consistent with the types of adverse events known for the drug;
- Whether the suspected adverse event can be explained by the effects of the combined drug, the patient's clinical condition, or the effects of other therapies;
- Whether the suspected adverse event resolved or abated after discontinuation or dosage reduction;
- Whether the same reaction recurred after re-exposure to the suspected drug.

Criteria for determining causality: based on the order of the above 5 judgment indicators

Judgment results	Judgment Indicators				
	1	2	3	4	5
Definitely relevant	+	+	--	+	+
Possibly related	+	+	--	+	?

Uncertain	+	+	±	±	?
Possibly not related	+	--	±	±	?
Definitely not	--	--	+	--	--

Explanation: + Affirmative, - Negative, ± Difficult to affirm or deny, ? Circumstances unknown. Based on the table above, determine the relationship between the following 5 levels of adverse events and drugs

- Definitely related, 2 - possibly related, 3 - unable to determine, 4 - possibly unrelated, 5 - definitely unrelated.

The incidence of adverse events was calculated using the total number of cases 1+2+3 as the numerator and all the enrolled cases available for adverse event evaluation as the denominator.

